[figure not shown]
[figure not shown]
[figure not shown]
[figure not shown]

Protocol for non-interventional studies based on existing data

Document Number:	c30035684-01
BI Study Number:	1237-0092
BI Investigational Product(s):	Not applicable
Title:	Real-world treatment of newly diagnosed COPD patients: A retrospective German claims data analysis
Protocol version identifier:	1.0
Date of last version of protocol:	16 October 2019
PASS:	No
EU PAS register number:	Not applicable
Active substance:	ATC code group R03
Medicinal product:	Not applicable
Product reference:	Not applicable
Procedure number:	Not applicable
Joint PASS:	No
Research question and objectives:	
 A. Description of the real-life drug treatment of patients with incident COPD, including description of treatment sequence/escalation in the first 12/24/36 months after incident diagnosis B. Comparison of initial drug treatment of incident COPD patients with two versions of German treatment guidelines (2012/2018) C. Description of exacerbation frequency (severe exacerbations associated with an inpatient hospitalization) of incident COPD patients in the first 12/24/36 months after incident diagnosis

Proprietary confidential information © 2019 Boehringer Ingelheim International GmbH or one or more of its affiliated companies

	D. Description of health-care resource use (HCRU; including use of oxygen therapy) and direct treatment cost of incident COPD patients in the first 12/24/36 months after incident diagnosis 
Country(-ies) of study:	Germany
Author:	
Marketing authorisation holder(s):	
MAH contact person:	
In case of PASS, add: <EU-QPPV:>	Not applicable
In case of PASS, add: <Signature of EU-QPPV:>	Not applicable
Date:	16 October 2019

Page 1 of 58

Proprietary confidential information

© 2019 Boehringer Ingelheim International GmbH or one or more of its affiliated companies. All rights reserved.
This document may not - in full or in part - be passed on, reproduced, published or otherwise used without prior written permission

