4. ABSTRACT

Name of company: Boehringer Ingelheim			
Name of finished medicinal product: COPD medication of any type			
Name of active ingredient: COPD medication of any type, ATC code R03			
Protocol date: 16 Oct 2019	Study number: 1237-0092	Version/Revision: 1.0	Version/Revision date: Not applicable
Title of study:	Real-world treatment of newly diagnosed COPD patients: A retrospective German claims data analysis		
Rationale and background:	
In terms of COPD drug therapy, the current German COPD guideline (S2) [1, 2] recommends a treatment escalation procedure. For incident COPD patients (for the sake of simplicity, newly diagnosed and so far treatment naïve COPD patients will be referred to as “incident COPD patients” in the following), the German guideline recommends the following:
 
 • No treatment (low symptom burden) • SABA or SAMA • LABA or LAMA or LABA+LAMA. 
All other treatments, particularly combination treatments including ICS¹, are only recommended as escalation therapy.
 
Currently, knowledge on real world treatment of incident COPD patients in Germany is sparse, in particular regarding the frequency of different drug therapy prescriptions and the frequency of early therapy escalation including ICS.
 
This study aims to address this issue by reporting treatment of incident COPD patients in the real world. COPD and treatment associated outcomes, especially severe exacerbations (leading to hospitalization), health-care resource use, and early use of oxygen therapy, will be explored. In addition, real-world treatment of incident COPD patients will be compared to German guidelines, using current 2018 guidelines and 2012 guidelines as framework in two scenario calculations.
		

¹ ICS is recommended by the guideline for COPD patients with an asthmatic component. Based on inclusion/exclusion criteria as applied in this study, these patients will be excluded from analysis.

Name of company: Boehringer Ingelheim			
Name of finished medicinal product: COPD medication of any type			
Name of active ingredient: COPD medication of any type, ATC code R03			
Protocol date: 16 Oct 2019	Study number: 1237-0092	Version/Revision: 1.0	Version/Revision date: Not applicable

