
 Previous drug treatment in the pre-index period, based on appropriate ATC group level 
 Percentage of patients who received specific treatments (most common 10 treatments as observable for above samples) with at least two prescriptions in the pre-index period. 
Documentation referring to the 12 months follow-up after index date (for patient subgroups: 24 months/36 months follow-up, or complete follow-up period)
 
 For patients with available data resulting from a disease management program (DMP) 
 Weight [kg] (reported MIN, MAX and MEAN during follow-up period) Height [cm] Blood pressure (reported MIN, MAX and MEAN during follow-up period) Non-drug treatment recommendations Exacerbations (number and severity) FEV₁ (reported MIN, MAX and MEAN during follow-up period) Smoking status if applicable Drug treatment with long-acting bronchodilators (incl. separate reporting for respective agent classes beta-agonists, anticholinergics, methylxanthines) Drug treatment with short-acting agents Drug treatment with anti-inflammatory drugs (ICS, PDE-4, macrolides) Top-10 prescribed non-COPD drug therapies (based on ATC codes on appropriate level) 			

Name of company: Boehringer Ingelheim			
Name of finished medicinal product: COPD medication of any type			
Name of active ingredient: COPD medication of any type, ATC code R03			
Protocol date: 16 Oct 2019	Study number: 1237-0092	Version/Revision: 1.0	Version/Revision date: Not applicable

 • Antibiotics for systemic use (based on ATC J02AA) • Antibiotics in combination with corticosteroids (based on ATC D07C) • Systemic/oral corticosteroids (SCS/OCS; based on ATC R01AD02; D07AA01; D10AA02; H02AB04) • All-cause hospitalizations 
 ○ Among them: hospitalizations with COPD as main diagnosis (ICD-10 J44.-) • Among them: hospitalizations with a COPD exacerbation as main diagnosis (ICD-10 J44.1) • Exacerbations as documented by outpatient pneumologists (ICD-10 J44.1) • GP visits and pneumologists' visits and visits to other specialists • Prescription of COPD-associated aids 
 ○ Oxygen therapy • Date of death, if patient died during follow-up period (for censoring and time to event analyses). 			

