9.2 SETTING

An anonymized dataset from the cooperating sickness funds, which includes all patients with at least one COPD diagnosis, who were insured by this sickness funds for the entire period (01/01/2013 - 30/06/2018) will be available.

A patient will be confirmed as being COPD-incident if specialists documented at least two confirmed outpatient COPD diagnoses (ICD J44.-) and/or at least one inpatient COPD diagnosis (ICD J44.-), without such diagnoses in the previous 12 months and without any COPD prescription in the previous 12 months (Suppl. Table 2).

Specific inclusion criteria can be described as follows:

- All patients should have been covered by the sickness fund for the entire period (01/01/2013-30/06/2018) or, in case a patient deceased after index date, for the time until death
- A patient will be included as an incident COPD patient if either a hospital documented at least one COPD diagnosis (ICD-10 J44.-) or a specialist (pneumologist) documented at least two confirmed COPD diagnoses (above ICD-10 code) in two different quarters; the first of the above diagnoses is defined as index diagnosis; inclusion period is defined as lasting from 01/01/2014 until 30/06/2017

- Patients should not have received any COPD diagnosis (ICD-10 J44.-) or any COPD-associated medication (Suppl. Table 2)⁹ in the 12 months pre-index period
- Patient should have, at date of incident COPD diagnosis (index date), an age of at least 40 years

Patients who received at least one confirmed inpatient asthma diagnosis or two confirmed outpatient diagnoses of asthma (ICD-10: J45.-) by pneumologists after the incident COPD diagnosis (index diagnosis) will be separately observed.

Based on these inclusion/exclusion criteria, the following data sets will be analyzed (Figure 3)¹⁰:

- COPD-FULL DATA: All incident COPD patients with a follow-up of up to 54 months
- COPD-12: All incident COPD patients with a follow-up¹¹ of 12 months since index date
- COPD-24: All incident COPD patients with a follow-up of 24 months since index date
- COPD-36: All incident COPD patients with a follow-up of 36 months since index date
- COPD DMP-FULL DATA: All incident COPD patients with available DMP data (at least one entry during 3 months after index date¹²) and a follow-up of up to 54 months.
- COPD DMP-12: All incident COPD patients with available DMP data (at least one entry during 3 months after index date) and a follow-up of 12 months since index date

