Supplemental Table 2: COPD medications available in the German market

Medication class	Agents	ATC-Codes
SABA	Salbutamol	R03AC02
	Terbutaline	R03AC03
	Fenoterol	R03AC04; R03CC04
	Reprotoerol	R03CC14; R03AC15
LABA	Salmeterol	R03AC12
	Formoterol	R03AC13
	Indacaterol	R03AC18
	Olodaterol	R03AC19
	Bambuterol	R03CC12
	Clenbuterol	R03CC13
LABA-combi	Clenbuterol, combinations	R03CC63
SABA-combi	Fenoterol and sodium cromoglycate	R03AK03
	Salbutamol and sodium	R03AK04
	Reprotoerol and sodium	R03AK05
ICS+LABA	Salmeterol and fluticasone	R03AK06; R03AK61
	Formoterol and budesonide	R03AK07; R03AK28;
	Formoterol and beclometasone	R03AK08; R03AK27;
	Vilanterol and fluticasone furoate	R03AK10
	Formoterol and fluticasone	R03AK11
SABA+SAMA	Fenoterol and ipratropium bromide	R03AL01
	Salbutamol and ipratropium	R03AL02
LABA+LAMA	Vilanterol and umeclidinium	R03AL03
	Indacaterol and glycopyrronium	R03AL04
	Formoterol and aclidinium bromide	R03AL05
	Olodaterol and tiotropium bromide	R03AL06
ICS	Beclometasone	R03BA01; R01AD01
	Budesonide	R03BA02; R01AD05
	Fluticasone	R03BA05; R01AD08
SAMA	Ipratropium bromide	R03BB01; R01AX03
LAMA	Tiotropium bromide	R03BB04
	Aclidinium bromide	R03BB05
	Glycopyrronium bromide	R03BB06
	Umeclidinium	R03BB07
LAMA+LABA+ICS	Glycopyrronium and Formoterol	R03AL09

Medication class	Agents	ATC-Codes
Methylxanthine	Theophylline	R03DA04
	Aminophylline	R03DA05
PDE-4	Roflumilast	R03DX07
Systemic/oral corticosteroids ¹	Prednisolone	R01AD02
	Methylprednisolone	D07AA01; D10AA02;

¹for exacerbations

Supplemental Table 3: Calculation of the Charlson Comorbidity Index (CCI)

No	Comorbidity	Charlson Score	ICD-10 Code
1	Coronary artery disease	1	I20.-, I21.-, I22.-, I23.-, I24.-, I25.-
2	Congestive heart failure	1	I11.-, I50.-
3	Peripheral vascular disease	1	I73.-, I74.-, I77.-
4	Cerebrovascular disease	1	G45.-, G46.-, I6.-
5	Dementia	1	F00.-, F01.-, F02.-, F03.-, G30.-
6	Chronic pulmonary disease	1	J4.-, J6.- w/o J67.-, J68.-, J69.-
7	Connective tissue disorder	1	M05.-, M06.-, M07.-, M08.-, M3.-
8	Peptic ulcer disease	1	K25.-, K26.-, K27.-, K28.-
9	Mild liver disease	1	B18.-, K70.-, K73.-, K75.-
10	Diabetes mellitus without complications	1	E109.-, E119.-, E129.-, E139.-, E149.-
11	Hemiplegia	2	G81.-, G82.-
12	Moderate or severe renal disease	2	N17.-, N18.-, N19.-
13	Diabetes mellitus with end-organ damage	2	E10.-, E11.-, E12.-, E13.-, E14.- w/o [No 10]
14	Tumor without metastases, leukemia, lymphoma, multiple myeloma	2	C% w/o [No 16]

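### Supplemental Table 2 counts three R01AD codes as ICS and R01AX03 as SAMA, outside the declared R03 scope and with no route rule, while R01AD02 is classed as systemic/oral

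*Combined protocol and SAP*

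**What the plan says.** The title page gives the active substance as "ATC code group R03" and the abstract header gives "COPD medication of any type, ATC code R03". The working definition of COPD medication is Supplemental Table 2 in Annex 3. Under ICS it lists beclometasone as "R03BA01; R01AD01", budesonide as "R03BA02; R01AD05" and fluticasone as "R03BA05; R01AD08". Under SAMA it lists ipratropium as "R03BB01; R01AX03". R01AD02 (prednisolone) stands in the systemic/oral row, and the abstract's variable list repeats this: "Systemic/oral corticosteroids (SCS/OCS; based on ATC R01AD02; D07AA01; D10AA02; H02AB04".

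Section 9.2 applies the table at entry: "Patients should not have received any COPD diagnosis (ICD-10 J44.-) or any COPD-associated medication" in the 12 months before index. Footnotes in the abstract and in section 9.2 exempt systemic/oral corticosteroids (SCS/OCS) from this exclusion. Neither the table nor any section says which route or dosage form an R01 code must have in order to count.

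**The concern.** One ATC subgroup, R01AD, is counted as inhaled for three agents and as systemic/oral for a fourth, and four codes lie outside the stated scope, with no reason given. How early and how often ICS is prescribed is the question the study asks, so the ICS class should be its least ambiguous variable. As written, the code list decides who counts as treatment-naïve, who counts as an ICS user after index, and what counts as COPD drug cost. A reader of the results could not tell which prescriptions those terms cover.

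**Working it through.** **1. Code count (legible text of Supplemental Table 2, without the SCS/OCS row).** SABA 6, LABA 6, LABA-combi 1, SABA-combi 3, ICS+LABA 8, SABA+SAMA 2, LABA+LAMA 4, ICS 6, SAMA 2, LAMA 4, triple 1, methylxanthine 2, PDE-4 1: total 46. R03 codes: 42. The other four are R01AD01, R01AD05, R01AD08 and R01AX03, each beside an R03 code for the same agent. That is 3 of 6 single-agent ICS codes and 1 of 2 SAMA codes.

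**2. Where the codes act.**

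| Use | R01AD01/05/08 | R01AX03 | R01AD02 |
|---|---|---|---|
| 12-month drug-free criterion (9.2) | excludes | excludes | exempt |
| Agent list (9.3.2.1) | counts | counts | counts |
| ICS treatment lines, Table 2 (9.3.2.1) | counts | no | no |
| Time to therapy including ICS (9.7.1, Table 4) | counts | no | no |
| 2018 index-date criterion (9.3.2.2) | counts | no | no |
| COPD drug counts and cost (Table 3) | counts | counts | counts |
| Non-severe exacerbation proxy (9.3.2.2) | no | no | counts |

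The ICS entries assume that ICS is read from Supplemental Table 2, the only ICS code list in the protocol. The SCS/OCS exemption covers entry only. The agent list and Table 3 draw on the whole table, so R01AD02 enters both.

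The first part of Table 2 has 3 + 6 = 9 monotherapy rows. Five have ICS as a line of its own (ICS; LAMA to ICS; LABA to ICS; ICS to LABA; ICS to LAMA) and need no combination rule. An R01AD item enters a dual or triple pattern only if the combination rule is met with another agent.

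**3. Illustrative size.** The documents give no code frequencies. All shares of 1%, 5% and 10% are assumptions.

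- *ICS monotherapy.* Section 9.5 gives about 26,000 of 40,000 with a long-acting bronchodilator in 12 months (26,000/40,000 = 65%, as stated), leaving 14,000. If those shares of the 14,000 have an R01AD01/05/08 item and no R03 ICS: 14,000 × 0.01, 0.05, 0.10 = 140, 700, 1,400 patients, or 0.35%, 1.75%, 3.5% of 40,000. Against the 5% reporting threshold, the row would cross only if R03 ICS alone already put more than 4.65%, 3.25% or 1.5% there.
- *ICS at index + 4 weeks.* With those shares a as yearly starters, spread evenly, and true ICS share p, the increase is (1 − p) × a × 28/365. The half-width is 1.96 × √(p(1 − p)/40,000).

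| Assumed p | Increase at 1% / 5% / 10% (points) | 95% CI half-width (points) |
|---|---|---|
| 10% | 0.07 / 0.35 / 0.69 | 0.29 |
| 20% | 0.06 / 0.31 / 0.61 | 0.39 |
| 40% | 0.05 / 0.23 / 0.46 | 0.48 |

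 If instead 1% or 5% had such an item inside the four-week window itself, p + (1 − p)q moves 20% to 20.8% or 24.0%. That is less plausible, because the same table has already removed anyone with one of these codes in the previous 12 months.
- *Entry.* If a share w of otherwise eligible patients had an R01 code as their only listed drug, and the feasibility count already used these codes, 40,000 × w/(1 − w) = 404, 2,105 or 4,444 are already removed. If it did not, N falls to 40,000 × (1 − w) = 39,600, 38,000 or 36,000. At p = 20% the half-width goes from 0.392 to at most 0.413 points.

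**The case against.** The strongest reply is that no contradiction has been shown. No full code stands in two classes, and the documents never say what route R01AD or R01AX denotes. A reader who knows the ATC system might infer that these codes are simply the wrong route. The documents do not support that inference, and it is not made here. What remains is an unexplained split within one subgroup and a departure from the declared scope.

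Next, R03 appears only in header fields, Supplemental Table 2 is the operative definition, and D07, D10, H02 and J02 codes are used elsewhere. It is true that R03 does not limit every drug analysed. But those other codes belong to the steroid and antibiotic variables. Within the COPD drug classes the four R01 codes are the only legible exceptions. The count is of legible text: the SCS/OCS row and two ICS+LABA rows end in a semicolon and may be cut.

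It can also be said that a wider drug-free criterion suits a treatment-naïve cohort, that every rate above is assumed, and that most resulting shifts are small. All of that stands. A reader might infer that the cohort is biased or materially smaller, but neither is shown.

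Finally, the extraction manual (section 9.4) may yet set a route. It is still to be agreed, so it does not settle the point, though it is the natural place for the rule.

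**Conclusion.** The point holds as a code-list defect that reaches the cohort definition and the primary outcome, and it should be fixed before extraction. R01AD01, R01AD05 and R01AD08 act as ICS throughout. R01AX03 is a scope mismatch only, touching entry, the agent list, and drug counts and cost. R01AD02 sits in another class from its subgroup and feeds the agent list, drug counts and cost as well as the exacerbation proxy.

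The size is unknown. Under the assumed shares, ICS monotherapy gains 0.35% to 3.5% of the cohort and the loss of precision is small. The effect on the index-date guideline check is probably small. The effects on cost and on time to therapy including ICS cannot be sized from the documents.

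One might also infer that a listed SCS/OCS code is wrong, or that prednisolone lacks a systemic code. The documents do not support either: H02AB04 is in the abstract's list and the table row looks cut.

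**What to change.** Before the extraction manual is agreed:

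1. Define ICS and SAMA by their R03 codes in the main analysis, in line with the declared scope. This rests on the scope statement, not on a view of what route R01 denotes. If an R01 code is kept in the main analysis, give the reason for that code.
2. Repeat the drug-free exclusion count and the ICS outcomes, including the ICS monotherapy rows, with the R01 codes as a sensitivity analysis.
3. Verify the route of every SCS/OCS code by ATC and PZN (section 9.1, Table 1 lists PZN as available). Apply the result wherever those codes are used: proxy, agent list, drug counts and cost.
4. In the attrition chart already planned in the abstract, report how many patients are excluded by an R01 code alone.

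The cost is a code-list edit, one sensitivity run, one line in the attrition chart, and possibly a rerun of the N>40,000 feasibility count if it used the current codes.
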